Appendix 4. Response Evaluation Criteria in Solid Tumours (RECIST), Version 1.1

This scale is used for the assessment of extracranial response.

Measurability of Tumour at Baseline

Definitions

At baseline, tumour lesions/lymph nodes will be categorized measurable or non-measurable as follows:

Measurable

Tumour lesions: Must be accurately measured in at least one dimension (*longest* diameter in the plane of measurement is to be recorded) with a *minimum* size of:

- 10 mm by CT scan (CT scan slice thickness no greater than 5 mm);
- 10 mm caliper measurement by clinical examination (lesions which cannot be accurately measured with calipers should be recorded as non-measurable);
- 20 mm by chest X-ray.

Malignant lymph nodes: To be considered pathologically enlarged *and* measurable, a lymph node must be ≥ 15 mm in *short* axis when assessed by CT scan (CT scan slice thickness recommended to be no greater than 5 mm). At baseline and in follow-up, only the *short* axis will be measured and followed.

Non-Measurable

All other lesions, including small lesions (longest diameter < 10 mm or pathological lymph nodes with ≥ 10 to < 15 mm short axis) as well as truly non-measurable lesions. Lesions considered truly non-measurable include: leptomeningeal disease, ascites, pleural or pericardial effusion, lymphangitic involvement of skin or lung, abdominal masses/abdominal organomegaly identified by physical examination that is not measurable by reproducible imaging techniques.

Special Considerations Regarding Lesion Measurability

Bone lesions, cystic lesions and lesions previously treated with local therapy require particular comment:

Bone lesions:

- Bone scan, PET scan or plain films are not considered adequate imaging techniques to measure bone lesions. However, these techniques can be used to confirm the presence or disappearance of bone lesions.
- Lytic bone lesions or mixed lytic-blastic lesions, with *identifiable soft-tissue components*, that can be evaluated by cross sectional imaging techniques such as CT

or MRI can be considered measurable lesions if the *soft-tissue component* meets the definition of measurability described above.

- Blastic bone lesions are non-measurable.

Cystic lesions:

- Lesions that meet the criteria for radiographically defined simple cysts should not be considered as malignant lesions (neither measurable nor non-measurable) since they are, by definition, simple cysts.

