If a new lesion is equivocal, for example because of its small size, continued therapy and follow-up evaluation will clarify if it represents truly new disease. If repeat scans confirm there is definitely a new lesion, then progression should be declared using the date of the initial scan.

While FDG-PET response assessments need additional study, it is sometimes reasonable to incorporate the use of FDG-PET scanning to complement CT scanning in assessment of progression (particularly possible 'new' disease). New lesions on the basis of FDG-PET imaging can be identified according to the following algorithm:

1. Negative FDG-PET at baseline, with a positive FDG-PET at follow-up is a sign of PD based on a new lesion. A 'positive' FDG-PET scan lesion is one which is FDG avid with an uptake greater than twice that of the surrounding tissue on the attenuation corrected image.
2. No FDG-PET at baseline and a positive FDG-PET at follow-up:

If the positive FDG-PET at follow-up corresponds to a new site of disease confirmed by CT, this is PD.

If the positive FDG-PET at follow-up is not confirmed as a new site of disease on CT, additional follow-up CT scans are needed to determine if there is truly progression occurring at that time (if so, the date of PD will be the date of the initial abnormal FDG-PET scan).

If the positive FDG-PET at follow-up corresponds to a pre-existing site of disease on CT that is not progressing on the basis of the anatomic images, this is not PD.

Evaluation of Best Overall Response

The best overall response is the best response recorded from the start of the study treatment until the end of treatment taking into account any requirement for confirmation. On occasion a response may not be documented until after the end of therapy so protocols should be clear

if post-treatment assessments are to be considered in determination of best overall response. Protocols must specify how any new therapy introduced before progression will affect best response designation. The patient's best overall response assignment will depend on the findings of both target and non-target disease and will also take into consideration the appearance of new lesions. Furthermore, depending on the nature of the study and the protocol requirements, it may also require confirmatory measurement. Specifically, in non-randomised trials where response is the primary endpoint, confirmation of PR or CR is needed to deem either one the 'best overall response'.

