In some circumstances it may be difficult to distinguish residual disease from normal tissue. When the evaluation of complete response depends upon this determination, it is recommended that the residual lesion be investigated (fine needle aspirate/biopsy) before assigning a status of complete response. FDG-PET may be used to upgrade a response to a CR in a manner similar to a biopsy in cases where a residual radiographic abnormality is thought to represent fibrosis or scarring. The use of FDG-PET in this circumstance should be prospectively described in the protocol and supported by disease specific medical literature for the indication. However, it must be acknowledged that both approaches may lead to false positive CR due to limitations of FDG-PET and biopsy resolution/sensitivity.

For equivocal findings of progression (e.g., very small and uncertain new lesions; cystic changes or necrosis in existing lesion), treatment may continue until the next scheduled assessment. If at the next scheduled assessment, progression is confirmed, the date of progression should be the earlier date when progression was suspected.

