Appendix 5. Modified Response Evaluation Criteria in Solid Tumors (mRECIST), Version 1.1

This scale is used for the assessment of brain lesion response.

Modifications to RECIST v1.1 for Assessment of Brain Lesions

The modifications to RECIST v1.1 impact the number and the minimal size of the target brain lesions selected at baseline. Up to 5 lesions may be selected as target lesions; all brain lesions beyond these 5 target lesions will be regarded as nontarget lesions. Measurable lesions are defined as those that can be accurately measured in at least 1 dimension with the longest diameter ≥ 5 mm when evaluated with gadolinium-enhanced MRI.

Gadolinium-enhanced MRI is the only imaging modality accepted for the assessment of brain lesions.

- The technical specification of the MRI scanning sequence will be optimized for the evaluation of brain lesions, which must be measured in the same anatomic plane using the same imaging examinations. Whenever possible the same scanner should be used ([Eisenhauer et al, 2009](#)).
- As a modification to RECIST v1.1, target lesions as small as 5 mm may be selected, however the scanning should follow RECIST v1.1: contiguous slices of maximum thickness corresponding to half the size of the lesion. All measurements must be taken and recorded in millimeters (mm) using a ruler or calipers.
- Image Acquisition guidelines provide the slice thickness requirements that should be used following RECIST v1.1 criteria.

Evaluation of Target Brain Lesions

Definitions for assessment of target brain lesion(s) are as follows:

Complete Response (CR): Disappearance of all target lesions.

Partial Response (PR): At least a 30% decrease in the sum of diameters of target lesions, taking as reference the baseline sum diameters (e.g., percent change from baseline).

Stable Disease (SD): Neither sufficient shrinkage to qualify for PR nor sufficient increase to qualify for PD.

Progressive Disease (PD): At least a 20% increase in the sum of diameters of target lesions, taking as reference the *smallest sum of diameters* recorded since the treatment started (e.g., percent change from nadir, where nadir is defined as the smallest sum of diameters recorded since treatment start). In addition, the sum must have an absolute increase of at least 5 mm.

Not Evaluable (NE): Cannot be classified by 1 of the 4 preceding definitions.

Special Notes on the Assessment of Target Brain Lesions

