If a target brain lesion disappears and reappears at a subsequent time point it should continue to be measured. The response at the time when the lesion reappears will depend upon the status of other lesions. For example, if the disease had reached a CR status then PD would be documented at the time of reappearance. However, if the response status were PR or SD, the diameter of the reappearing lesion should be added to the remaining diameters and response determined based on percent change from baseline and percent change from nadir.

Evaluation of Non-target Brain Lesions

Definitions for assessment of non-target brain lesion(s) are as follows:

Complete Response (CR): Disappearance of all non-target lesions.

Non-CR/Non-PD: The persistence of 1 or more non-target lesion(s) identified as a site of disease.

Progressive Disease (PD): Unequivocal progression of existing non-target lesions.

Not Applicable (NA): No non-target brain lesions at baseline.

Not Evaluable (NE): Cannot be classified by 1 of the 4 preceding definitions.

Special Notes on the Assessment of Non-target Brain Lesions

Non-target brain lesions that are not assessed at a particular timepoint based on the SoA (Table 3) should be excluded from the response determination (e.g., non-target response does not have to be “Not Evaluable”).

New Lesions

New brain malignancies denoting disease progression must be unequivocal. Lesions identified in follow up in an anatomical location not scanned at baseline are considered new lesions.

Any equivocal new lesion should continue to be followed. Treatment can continue at the discretion of the Investigator until the next scheduled assessment. If at the next assessment the new lesion is considered to be unequivocal, progression should be documented.

Time Point Response for Brain Lesions

Table A3 presents the intracranial response at an individual time point for all possible combinations of tumor response in target and non-target brain lesions, with or without the appearance of new brain lesions for patients with measurable (as defined in Section 7.2.1 and Section 7.2.2) intracranial disease at baseline.

Patients with a global deterioration of health status that requiring discontinuation of treatment without objective evidence of disease progression at that time should be classified as having

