6.1. Primary Endpoints

6.1.1. Safety Lead-in

The number and proportion of patients experiencing DLTs during Cycle 1 will be summarized by SOC and PT based on maximum toxicity grade. Analyses of DLT will be performed on Dose-determining Set.

All DLTs and their attributes will be presented in data listings sorted by patient identifier, AE and date of onset of the AE.

6.1.2. Phase 2

Main Analysis:

BMRR will be calculated by dividing the number of patients with a BOR of confirmed CR or confirmed PR in brain metastasis by the number of patients in the Efficacy Set in the respective cohort. The corresponding exact Clopper-Pearson 2-sided 90% CI and 95% CI will be calculated.

BOR is defined as the best response recorded from date of the first dose of study treatment until progression by Investigator assessment at each time point. Only tumor assessments performed before the start of any subsequent anticancer therapies will be considered in the assessment of BOR. Clinical deterioration or clinical progression noted on the End of Study completion eCRF will not be considered as documented disease progression. BOR will be determined according to the following rules:

- CR = at least two determinations of CR at least 4 weeks apart and documented before progression and start of new anticancer therapy.
- PR = at least two determinations of PR or better (and not qualifying for a CR) at least 4 weeks apart and documented before progression and start of new anticancer therapy.
- SD (for patients with at least one measurable lesion at baseline)= at least one SD assessment (or better and not qualifying for CR or PR) ≥ 6 weeks after date of the first dose and before progression and start of new anticancer.
- Non-CR/Non-PD (for patients with only non-target disease at baseline) = at least one Non-CR/Non-PD assessment (or better and not qualifying for CR or PR) ≥ 6 weeks after date of the first dose and before progression and the start of new anticancer therapy.
- PD = progression ≤ 16 weeks after date of the first dose (and not qualifying for CR, PR or SD).
- Not Evaluable (NE) = all other cases.

The frequency (number and percentage) of patients with BOR in brain metastasis of CR, PR, SD, PD, non-CR/non-PD (applicable only to patients with non-measurable disease at baseline), and NE will be tabulated.

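### The brain criteria (Protocol Appendix 5) give no progression date when an equivocal new brain lesion later becomes certain, the extracranial criteria (Appendix 4) back-date it, and neither Appendix 6 nor the SAP settles which date counts

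*Protocol*

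**What the plan says.** **Brain lesions (Protocol Appendix 5, New Lesions).** A new lesion counts as progression only when it is certain: "New brain malignancies denoting disease progression must be unequivocal". An equivocal one is followed, treatment may continue at the Investigator's discretion, and "If at the next assessment the new lesion is considered to be unequivocal, progression should be documented". No date is attached to that progression.

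**Extracranial lesions (Protocol Appendix 4).** The opening line limits the scope: "This scale is used for the assessment of extracranial response". The rule is given twice. Under New Lesions: "If repeat scans confirm there is definitely a new lesion, then progression should be declared using the date of the initial scan". Under the special notes, for equivocal findings generally: "the date of progression should be the earlier date when progression was suspected".

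**Scope of the brain modification (Appendix 5, opening).** "The modifications to RECIST v1.1 impact the number and the minimal size of the target brain lesions selected at baseline". Dating of progression is not among the listed changes.

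**Global response (Appendix 6).** Table A4 has a column for new lesions, but the text has no rule for equivocal ones.

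**Derivation.** Appendix 5 has the Sponsor derive best overall brain response by program from the Investigator's response at each time point. SAP 6.1.2 takes the best response "until progression by Investigator assessment at each time point" and requires two determinations of PR or better at least 4 weeks apart, before progression. SAP 3.2.2.4 and 3.2.2.5 end DOR and PFS at the earliest documented progression or death. SAP 5.2.8 uses the earliest scan date within one evaluation; it does not link successive evaluations. The event and censoring table in SAP 6.2.4 has no row for back-dating.

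**The concern.** The two paragraphs on equivocal new lesions are parallel, but the brain version lacks the dating clause. Brain response is the primary endpoint, so the omission falls where it matters most.

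Two things are at stake. First, brain PFS and brain DOR depend on which scan carries the event, and global PFS can combine extracranial events dated to the first scan with brain events dated to the second. Second, the equivocal scan may itself be the one that confirms a PR. If progression is later dated back to that scan, the confirmation falls away. The same images can then give a responder or a non-responder, depending on a choice left to a site or a programmer.

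The study is open-label, the primary analysis uses Investigator assessment, and central review (Protocol 7.2.3) takes place only if judged necessary, so it cannot be counted on to impose one convention.

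**Working it through.** **1. The plan's own figure.** Exact binomial, n = 50, cut-off 21, BMRR 30% against 50% (Protocol 8.1 and 8.2). P(X ≥ 21 | 0.30) = 0.0478 and P(X ≥ 21 | 0.50) = 0.899. The stated 5% level and approximately 90% power reproduce. This point changes neither.

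**2. Scan grid (Protocol 1.3, Table 3).** Scans fall at C2D1, C3D1, every 8 weeks through Cycle 11, then every 12 weeks. Nominal days are 29, 57, 113, 169, 225 and 281 (C11D1), then 12-weekly.

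**3. Shift for one affected patient**, at 30.4375 days per month (SAP 5.2.11):

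| Interval between first sight and certainty | Days | Months |
|---|---|---|
| C2D1 to C3D1 | 28 | 28/30.4375 = 0.92 |
| 8-weekly, through Cycle 11 | 56 | 56/30.4375 = 1.84 |
| 12-weekly, after Cycle 11 | 84 | 84/30.4375 = 2.76 |

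Off-schedule scans are allowed (Protocol 7.2.1) and used in the efficacy analyses (SAP 5.2.7), so the interval can be shorter.

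**4. Worked patient A.** PR on day 29; target lesions still at PR plus an equivocal new brain lesion on day 57; lesion unequivocal on day 113. Formulas are those of SAP 6.2.4 and 6.2.5.

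| | Dated to day 113 | Dated to day 57 |
|---|---|---|
| Two PRs at least 4 weeks apart before PD | Yes (29 and 57, 28 days) | No |
| BOR | Confirmed PR | PD |
| PFS, months | 113/30.4375 = 3.71 | 57/30.4375 = 1.87 |
| DOR, months | (113 − 29 + 1)/30.4375 = 2.79 | Not defined |

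Under back-dating, BOR cannot be SD, because day 29 is before the 6-week minimum. Progression within 16 weeks makes it PD.

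**5. Worked patient B.** PR on day 57, equivocal on day 113, unequivocal on day 169. Later dating gives confirmed PR, PFS 169/30.4375 = 5.55 months and DOR (169 − 57 + 1)/30.4375 = 3.71 months. Back-dating gives PFS 3.71 months and BOR SD, since day 57 is past 6 weeks.

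**6. Cohort level (assumed shares; the documents give none).** If 5%, 10%, 20% or 30% of brain progressions start as equivocal new lesions, the mean shift per progression on 8-weekly scans is share × 1.84 = 0.09, 0.18, 0.37 or 0.55 months.

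For the 6-month brain PFS rate, assume exponential progression with median 6 months (182.6 days) and no other events. Six months falls between the scans on days 169 and 225, which are 168 and 224 days after first dose.
- Without the issue, the rate is exp(−ln 2 × 168/182.6) = 0.529.
- Patients first positive on the day-169 scan number exp(−ln 2 × 112/182.6) − 0.529 = 0.654 − 0.529 = 0.125.
- Later dating moves the affected share of these past 6 months. At 10%, 20% and 40% the rate becomes 0.541, 0.554 and 0.579, a rise of about 1, 2.5 and 5 points.

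**7. Primary test.** P(X ≥ 20 | 0.30) = 0.085 against 0.048 for 21. One reclassified patient decides the test if the count is at the threshold. That is true of any reclassification and does not measure how often this one occurs.

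**The case against.** The best defence is that Appendix 5 is silent rather than contrary. It does not instruct anyone to use the later date. Its opening sentence confines the modifications to the number and minimal size of target lesions, so the RECIST v1.1 back-dating could be taken as unchanged. The SAP's earliest documented progression does not force the later date either. This stands, and it rules out saying that the two appendices contain opposed rules. It does not remove the problem. Appendix 4 limits itself to extracranial disease, Appendix 5 writes its own paragraph on equivocal lesions, requires certainty before a lesion denotes progression, and feeds a time-point table and a programmed BOR. A programmer following that text would leave the equivocal scan as PR or SD.

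A reader might also infer that a response is being confirmed on a scan that already showed progression. The documents do not support that: the scan showed an equivocal lesion, which by Appendix 5 is not yet progression. Whether such a scan may confirm a response is a definition the plan has to make.

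Finally, PFS and DOR are descriptive Kaplan-Meier secondary endpoints and the cohorts are not formally compared, so no between-group contrast is biased. That is correct and limits the consequence. It does not cover confirmed BMRR, which is tested.

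**Conclusion.** The point holds as an unresolved dating rule in the criteria behind the primary endpoint. Later-scan dating is the more natural reading of Appendix 5; back-dating by carry-over is arguable; Appendix 6 and the SAP choose neither.

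The effect is confined to patients whose first brain progression is a new lesion called equivocal and then unequivocal. For them, brain PFS and DOR differ by 0.92, 1.84 or 2.76 months on the scheduled grid. A confirmed PR is at risk only if no earlier scan had already confirmed it. Target growth, non-target progression, clear new lesions and deaths are unaffected.

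A reader might infer that brain PFS and DOR as a whole run one interval longer, or might set 1.84 or 2.76 months against the 6.5-month median brain DOR that Protocol 2.1.3 cites for dabrafenib plus trametinib. Neither is supported: one patient's shift is not a shift in a cohort median, and the share affected is unknown. The cohort figures above (0.09 to 0.55 months in the mean; about 1 to 5 points in the 6-month rate) rest on assumed shares, and the rate also on an assumed 6-month median. Sample size, cut-off and power do not change. The matter should be settled before analysis because it can reclassify a responder and costs little to fix.

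**What to change.** - **Protocol Appendices 5 and 6:** add that, if an equivocal new lesion is confirmed as unequivocal, progression is dated to the scan on which it was first seen. This matches Appendix 4 and gives global response a single convention.
- **SAP 6.1.2, 6.2.4 and 6.2.5:** state that this date is used for BOR, DOR and PFS, so a scan on which such a lesion was first seen cannot confirm a response.
- **eCRF:** add a flag for equivocal new lesions, with the scan of first sight, so the rule can be programmed and the number of affected patients reported.
- **Sensitivity analysis:** repeat confirmed BMRR, brain and global DOR, and brain and global PFS with progression dated to the later scan.

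The cost is a few sentences, one data field and some programming. PFS, DOR and possibly confirmed BMRR become slightly less favourable. Treatment decisions and the visit and scan schedules are untouched, because the rule concerns only the date used in analysis.

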Appendix 6. Criteria for Evaluation of Global Response

This appendix provides definitions for global assessment of target and non-target lesion(s).

Evaluation of Target Lesions

Target lesion response is based on all (i.e., brain and extracranial) target lesions, up to a total of 10 lesions. The sum of longest diameters of all target lesions will be used to determine response. Definitions for assessment of response for target lesion(s), based on mRECIST v1.1 for brain lesion and RECIST v1.1 for extracranial lesions, are as follows:

Complete Response (CR): Disappearance of all target lesions. Any pathological lymph nodes must be < 10 mm on the short axis.

Partial Response (PR): At least a 30% decrease in the sum of the diameters of target lesions, taking as a reference the baseline sum of the diameters (e.g., percent change from baseline).

Stable Disease (SD): Neither sufficient shrinkage to qualify for PR nor sufficient increase to qualify for PD.

Progressive Disease (PD): At least a 20% increase in the sum of the diameters of target lesions, taking as a reference the smallest sum of diameters recorded since the treatment started (i.e., percent change from nadir, where nadir is defined as the smallest sum of diameters recorded since treatment start). In addition, the sum must have an absolute increase from nadir of at least 5 mm.

Not Applicable (NA): No extracranial target lesions at baseline.

Not Evaluable (NE): Cannot be classified by 1 of the 5 preceding definitions.

Special Notes on the Assessment of Target Lesions

If lymph nodes are documented as target lesions, the short axis is added to the sum of the diameters (i.e., sum of diameters is the sum of the longest diameters for non-nodal lesions and the short axis for nodal lesions). When lymph nodes decrease to non-pathological size (i.e., short axis < 10 mm), they should still have a measurement reported in order not to overstate progression.

If at a given assessment time point all target lesions identified as baseline are not assessed, the sum of diameters cannot be calculated for purposes of assessing CR, PR or SD, or for use as the nadir for future assessments. However, the sum of the diameters of the assessed lesions and the percent change from nadir should be calculated to ensure that progression has not been documented. If an assessment of PD cannot be made, the response assessment should be NE.

All target lesions (nodal and non-nodal) should have their measurements recorded even when very small (e.g., 2 mm). If lesions are present but too small to measure, 5 mm should be

recorded and should contribute to the sum of the diameters unless it is likely that the lesion has disappeared, in which case 0 mm should be reported.

If a target lesion disappears and reappears at a subsequent time point it should continue to be measured. The response at the time when the lesion reappears will depend upon the status of the other lesions. For example, if the disease had reached a CR status then PD would be documented at the time of reappearance. However, if the response status was PR or SD, the diameter of the reappearing lesions should be added to the remaining diameters and response determined based on percent change from baseline and percent change from nadir.

Evaluation of Non-target Lesions

Non-target lesion response is based on all (that is, brain and extracranial) non-target lesions. Definitions for assessment of response for non-target lesions are as follows:

Complete Response (CR): The disappearance of all non-target lesions. All lymph nodes identified as a site of disease at baseline must be non-pathological (i.e., < 10 mm short axis).

Non-CR/Non-PD: The persistence of 1 or more non-target lesion(s) or lymph nodes identified as a site of disease at baseline \geq 10 mm short axis.

Progressive Disease (PD): Unequivocal progression of existing non-target lesions.

Not Applicable (NA): No brain or extracranial non-target lesions at baseline.

Not Evaluable (NE): Cannot be classified by 1 of the 5 preceding definitions.

Special Notes on the Assessment of Non-target Lesions

In the presence of measurable disease, progression on the basis of solely non-target disease requires substantial worsening such that even in the presence of SD or PR in target disease, the global tumor burden has increased sufficiently to merit discontinuation of therapy.

In the presence of non-measurable-only disease, consideration should be given to whether or not the increase in global disease burden is comparable in magnitude to the increase that would be required to declare PD for measurable disease.

Sites of non-target lesions that are not assessed at a particular time point based on the SoA (Table 3) should be excluded from the response determination (i.e., non-target response does not have to be “Not Evaluable”).

Time Point Response

Table A4 presents the response at an individual time point for all possible combinations of tumor responses in all brain and extracranial target and non-target lesions with or without the appearance of new lesions.

Patients with a global deterioration of health status that requiring discontinuation of treatment without objective evidence of disease progression at that time should be classified as having “symptomatic deterioration.” Objective response status is determined by evaluations of disease burden. Every effort should be made to document the objective progression even after discontinuation of treatment.

In some circumstances, it may be difficult to distinguish residual disease from normal tissue. When the evaluation of CR depends on this determination, it is recommended that the residual lesion be investigated (e.g., fine needle aspirate or biopsy) to confirm the CR.

Table A4: Evaluation of Global Response

Target Lesions	Non-target Lesions	New Lesions	Global Response
CR	CR or NA	No	CR
CR	Non-CR/Non-PD or NE	No	PR
PR	Non-PD or NA or NE	No	PR
SD	Non-PD or NA or NE	No	SD
NE	Non-PD or NA or NE	No	NE
PD	Any	Yes or No	PD
Any	PD	Yes or No	PD
Any	Any	Yes	PD

Best Overall Global Response: All Time Points

The best overall global response is the best response recorded from the start of treatment until progression of brain metastasis or extracranial disease and will be determined programmatically by the Sponsor based on the Investigator’s assessment of global response (brain metastasis and extracranial disease) at each time point. Only tumor assessments performed before the start of any subsequent anticancer therapies and not later than 30 days after last dose of study drug will be considered in the assessment of best overall global response. Clinical deterioration or clinical progression noted on the completion eCRF will not be considered as documented disease progression.

To be assigned a status of overall global stable disease (SD), follow-up disease assessment must meet the SD criteria at least once after the first dose of study treatment for a minimum of 6 weeks.

If the minimum time for SD is not met, the best response will depend on subsequent assessments. For example, if an assessment of PD follows the assessment of SD and SD does not meet the minimum time requirement, the best response will be PD. Alternatively, patients lost to follow up after an SD assessment who do not meet the minimum time criterion will be considered NE.

Appendix 7. Adverse Events: Definitions and Procedures for Recording, Evaluating, Follow-up, and Reporting

